### **8.2.3 Grading and Attribution**

#### **8.2.3.1 GRADING CRITERIA**

The study site will grade the severity of AEs experienced by CIT study subjects according to the criteria set forth in the most current version of the *CIT-TCAE*. This document provides a common language to describe levels of severity, to analyze and interpret data, and to articulate the clinical significance of all AEs.

AE severity will be graded on a scale from 1 to 5 according to the following standards in the *CIT-TCAE* manual:

Grade 1 = Mild AE.

Grade 2 = Moderate AE.

Grade 3 = Severe and undesirable AE.

Grade 4 = Life-threatening or disabling AE.

Grade 5 = Death.

AEs, not included in the CIT-TCAE listing, should be recorded and their severity graded from 1 to 5 according to the General Grade Definition provided below:

*Table 3: General severity definition of adverse event*

Grade 1	Mild	Transient or mild discomforts (< 48 hours), no or minimal medical intervention/therapy required, hospitalization not necessary (non-prescription or single-use prescription therapy may be employed to relieve symptoms, e.g., aspirin for simple headache, acetaminophen for post-surgical pain).
Grade 2	Moderate	Mild to moderate limitation in activity some assistance may be needed; no or minimal intervention/therapy required, hospitalization possible.
Grade 3	Severe	Marked limitation in activity, some assistance usually required; medical intervention/therapy required hospitalization possible.
Grade 4	Life-threatening	Extreme limitation in activity, significant assistance required; significant medical/therapy intervention required hospitalization or hospice care probable.
Grade 5	Death	Death.

All AEs will be reported and graded, by the PI or designee, whether they are or are not related to disease progression or treatment.

#### 8.2.3.2 DEFINITION OF ATTRIBUTION

Attribution will only be determined and collected for serious adverse events.

The relatedness, or attribution, of an AE to islet transplantation, which includes the transplant procedure and/or the islet product, to the immunosuppression and/or infection prophylaxis, or to the secondary investigational agent will be determined by the site investigator. The site investigator will also record the determination of attribution on the appropriate eCRF and/or SAE report form. The relationship of an AE (attribution of AE) to islet transplantation (islets or transplant procedure), immunosuppression/infection prophylaxis, or secondary investigational agent will be defined by using the descriptors provided below.

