- The incidence and severity of AEs related to the islet transplant procedure including: bleeding ( $> 2$  g/dL decrease in hemoglobin concentration); segmental portal vein thrombosis; biliary puncture; wound complication (infection or subsequent hernia); and increased transaminase levels ( $> 5$  times upper limit of normal [ULN])
- The incidence and severity of AEs related to the immunosuppression including: allergy; reduction in GFR; increase in urinary albumin excretion; addition or intensification of anti-hypertensive therapy; addition or intensification of anti-hyperlipidemic therapy; oral ulcers; lower extremity edema; gastrointestinal toxicity; neutropenia, anemia, or thrombocytopenia; viral, bacterial, or fungal infections; and benign or malignant neoplasms
- The incidence of a change in the immunosuppression drug regimen
- The incidence of immune sensitization defined by presence of anti-HLA antibodies absent prior to transplantation
- The incidence of discontinuation of immunosuppression

At  $365 \pm 14$  days following the first islet transplant:

- The incidence of worsening retinopathy as assessed by change in retinal photography from pre-transplant. If pupil dilation is not possible, then a manual ophthalmologic evaluation can be substituted.

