#### 4.1.2.2 SECONDARY SAFETY ENDPOINTS

- Safety, including incidence of post-transplant infections, malignancies, morbidity, and other AEs (e.g., increased body weight and hypertension) associated with conventional immunosuppression.
- Renal function as measured by serum creatinine, GFR and other relevant laboratory parameters.
- Lipid profiles (triglycerides, total cholesterol, LDL cholesterol, HDL cholesterol) over time.

At  $75 \pm 5$  days following each transplant, at  $365 \pm 14$  days following the first and final islet transplant, and at two years following the final islet transplant:

- The incidence and severity of AEs related to the islet transplant procedure including: bleeding (> 2 g/dL decrease in hemoglobin concentration); segmental portal vein thrombosis; biliary puncture; wound complication (infection or subsequent hernia); and increased transaminase levels (> 5 times upper limit of normal [ULN])
- The incidence and severity of AEs related to the immunosuppression including: allergy; reduction in GFR; addition or intensification of anti-hypertensive therapy;

- gastrointestinal toxicity; neutropenia, anemia, or thrombocytopenia; viral, bacterial, or fungal infections; and benign or malignant neoplasms
- The incidence of a change in the immunosuppression drug regimen
  - The incidence of immune sensitization defined by presence of anti-HLA antibodies absent prior to transplantation
  - The incidence of discontinuation of immunosuppression

At  $365 \pm 14$  days following the first islet transplant:

- The incidence of worsening retinopathy as assessed by change in retinal photography from pre-transplant. If pupil dilation is not possible, then a manual ophthalmologic evaluation can be substituted.

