### **6.2.2 Site Suspension and Review**

Study enrollment and initial islet transplants will be suspended (placed on hold) at a participating clinical site, pending expedited review of all pertinent data by the IRB, the NIAID, the NIDDK, and the NIDDK DSMB, if any one of the following occurs:

1. Any grade 5 AE that is possibly, probably, or definitely related to the study treatment regimen (Section 5); or
2. Two SAEs related to the islet transplant procedure (e.g., bleeding, thrombosis, gall bladder injury); or
3. Two consecutive primary non-functioning transplants (see Study Definitions).

After any site is placed on hold, no additional transplants will be performed at that site until the CIT Steering Committee and DSMB meet either in person or by conference call to review in depth the results and circumstances surrounding the islet functional failure or SAE to determine whether the trial enrollment of new subjects and conduct of additional transplants could be safely resumed at that site, or whether there could be implications for the continuation of the entire proposed pilot protocol also at other affiliated sites testing the same protocol.

In all cases of PNF, no further belatacept will be administered and subjects will be asked to temporarily continue on the standard immunosuppression to decrease the risk of sensitization that could increase the risk of poor outcome should future transplants occur. A tapering schedule will be applied until immunosuppressants are completely discontinued.

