**Table 4: Attribution of adverse events**

Code	Descriptor	Definition
UNRELATED CATEGORY		
1	Unrelated	The AE is clearly not related to the allogeneic islets; the islet transplant procedure; immunosuppression or infection prophylaxis; or secondary investigational agent.
RELATED CATEGORIES		
2	Unlikely	The AE is doubtfully related to the allogeneic islets; the islet transplant procedure; immunosuppression or infection prophylaxis; or secondary investigational agent.
3	Possible	The AE may be related to the allogeneic islets; the islet transplant procedure; immunosuppression or infection prophylaxis; or secondary investigational agent.
4	Probable	The AE is likely related to the allogeneic islets; the islet transplant procedure; immunosuppression or infection prophylaxis; or secondary investigational agent.
5	Definite	The AE is clearly related to the allogeneic islets; the islet transplant procedure; immunosuppression or infection prophylaxis; or secondary investigational agent.

For additional information and a printable version of the *CIT-TCAE* manual, consult the *CIT* website: <http://isletstudy.org>.

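### Attribution is collected only for serious adverse events, while two secondary safety endpoints count adverse events of any seriousness that are 'related to' the procedure or the immunosuppression

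*Protocol*

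**What the plan says.** All references are to the CIT04 protocol.

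- **Endpoints.** Section 4.1.2.2 lists "The incidence and severity of AEs related to the islet transplant procedure including" five named items, and "The incidence and severity of AEs related to the immunosuppression including: allergy; reduction in GFR; addition or intensification of anti-hypertensive therapy" and further items. The synopsis gives a longer list for the second endpoint: "The incidence and severity of AEs related to the immunosuppression including: allergy; reduction in GFR; increase in urinary albumin excretion" and more. Both endpoints are assessed around day 75 after each transplant, around day 365 after the first and final transplants, and two years after the final transplant. Section 2.1 makes safety part of the primary objective.
- **Collection.** Section 8.2.3.2 opens with "Attribution will only be determined and collected for serious adverse events". Section 8.2.2 has every AE recorded whatever its relation to treatment, and Section 8.2.3.1 has every AE graded.
- **Text pointing the other way.** The remainder of Section 8.2.3.2 describes how the investigator decides and records the attribution of an AE to three targets: islet transplantation (islets or procedure), immunosuppression or infection prophylaxis, and the secondary investigational agent. Section 8.2.1 asks for a new entry when the perceived relationship of an ongoing AE to study drug changes. Section 5.7.2, reason 4, covers any clinical AE or laboratory abnormality and refers to the agent to which it is attributed.
- **Meaning of 'related'.** Table 4 puts the code 'Unlikely' under its related categories, with the definition "The AE is doubtfully related to the allogeneic islets; the islet transplant procedure; immunosuppression or infection prophylaxis; or secondary investigational agent". Sections 6.2.1(1) and 6.2.2(1) name possible, probable and definite relation. Section 6.2.2(2) says only "Two SAEs related to the islet transplant procedure".

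The CIT08 follow-up protocol carries the same SAE-only sentence. None of its endpoints counts related AEs, so the conflict does not arise there.

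**The concern.** An endpoint that counts related events needs a relatedness value for every event that could qualify. Here that value exists only for serious events. The database will hold a severity grade for each AE and a causality judgement for a subset.

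The analyst then has three choices: report related SAEs under an endpoint that says AEs, report all AEs of the listed kinds as though they were related, or report nothing. The first understates the stated quantity and the second overstates it. In a pilot of 10 subjects, a handful of events separates the two. A causality judgement not made at the time is also hard to reconstruct later.

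**Working it through.** No sample size, power or error rate enters this point, so there is no stated figure to reproduce. The check is a comparison of texts, a count and one illustration.

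**1. Can the named events be non-serious?** Taking one item per semicolon:

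| Source | Procedure items | Immunosuppression items | Total |
|---|---|---|---|
| Section 4.1.2.2 | 5 | 7 | 12 |
| Synopsis | 5 | 11 | 16 |

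The synopsis adds four items: urinary albumin, anti-hyperlipidemic therapy, oral ulcers and lower extremity edema. Against the seriousness criteria in Section 8.1.2 (death, threat to life, hospitalization, disability and so on), none of the 12 or 16 items is serious by its own definition. A hemoglobin fall above 2 g/dL, transaminases above 5 times ULN, neutropenia or an added anti-hypertensive drug can each occur without meeting any criterion. In that case Section 8.2.3.2 leaves it without attribution.

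**2. What can be computed?** For either endpoint, and for a fixed list of event types,

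subjects with a related SAE ≤ subjects with a related AE ≤ subjects with any AE of those types.

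The endpoint is the middle term. The plan as written supplies the outer two.

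**3. How far apart can these be?** The only figures in the protocol are from the phase II renal study (Table 1.3.4.4A):

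| Arm | Related SAE | Related AE | Any AE |
|---|---|---|---|
| Belatacept MI, N=74 | 20 (27.0%) | 43 (58.1%) | 73 (98.6%) |
| Belatacept LI, N=71 | 23 (32.4%) | 40 (56.3%) | 69 (97.2%) |

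Assuming that subjects with a related SAE are a subset of those with a related AE, the share of related-AE subjects without a related SAE is

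- MI: (43 − 20)/43 = 23/43 = 0.535
- LI: (40 − 23)/40 = 17/40 = 0.425

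These counts cover AEs of every type in kidney recipients, not the listed types in islet recipients. They show that the gap can be wide. They do not estimate it here.

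**4. Meaning of 'related'.** By the heading in Table 4, codes 2 to 5 are related. By the wording of 6.2.1(1) and 6.2.2(1), the grades that count are codes 3 to 5. Section 6.2.2(2) does not say which applies, so two procedure SAEs coded 'Unlikely' meet it on one reading and not on the other. The post-treatment SAE text in Sections 8.2.2 and 8.3.1 also uses 'certainly', which is not a Table 4 descriptor.

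**The case against.** The best defence is that much of the safety picture survives. All AEs are recorded and graded. Several items are fixed by type or threshold (hemoglobin fall, transaminases, GFR, biliary puncture, portal vein thrombosis, added anti-hypertensive therapy), and the schedules of events and medication records supply the data. A SAP could tabulate these by type. For the procedure list, the type of event often nearly settles the cause. The sentence in 8.2.3.2 is contradicted by neighbouring text, so it may be a drafting slip rather than a settled ban. The primary endpoint and SAE attribution are untouched.

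Most of that stands, and it limits the point. It does not remove it. A tabulation by type is a different quantity from related events, the protocol states no such rule, and both lists are open-ended. The defence is weaker for the immunosuppression list: anemia, infection or gastrointestinal toxicity may have other causes. A SAP can choose how to analyse attribution but cannot create it.

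A reader might go further in four ways that the documents do not support:

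- **That most named events will be non-serious.** No serious/non-serious split is given, and Section 1.5.4.3 describes procedural bleeds that were reported to the registry as SAEs.
- **That 42% to 53% of subjects with related events would be missed here.** Those are the renal shares. The SAEs in that study also include frequent transplant rejection (18 of 74 and 20 of 71), which neither endpoint names.
- **That SAE-only attribution weakens the suspension rules.** The rules that use relatedness concern fatal, life-threatening or serious events, and 6.2.1(1) and 6.2.2(1) spell out their grades.
- **That 'Unlikely' SAEs will be counted as related in the endpoints.** No endpoint text says so. It follows only from a table heading.

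**Conclusion.** The conflict is real and should be corrected. The plan defines two secondary safety endpoints on a variable that it says is neither determined nor collected for non-serious events, and other sections assume that it is. As written, the endpoints reduce to related SAEs or cannot be computed as worded.

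The size in this trial is unknown. The conclusion rests on two things: the SAE-only sentence is followed as it stands, and 'AEs' in the endpoints means AEs of any seriousness, which is how both places word it. If sites instead followed the later text of 8.2.3.2 and recorded attribution for all AEs, the data would exist and only the wording would be wrong.

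The primary endpoint and its analysis are unaffected. The Table 4 matter is separate and smaller. It leaves Section 6.2.2(2) open to two readings, and the passages have to be reconciled.

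**What to change.** Choose one of two changes, and apply it in both Section 4.1.2.2 and the synopsis.

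1. **Drop relatedness from the endpoints.** Define both as the incidence and severity of listed event types regardless of attribution. This is wording only. It needs one closed list, so the 12-item and 16-item versions must be aligned. The cost is that the endpoints will include events unrelated to treatment, and they should be labelled accordingly.
2. **Collect attribution for all AEs.** Delete the SAE-only sentence in 8.2.3.2 and record attribution to each of its three targets. The cost is a few extra eCRF fields and investigator judgements for 10 subjects. The endpoint text should then say which targets feed which endpoint, because 8.2.3.2 lists belatacept (the secondary agent) apart from immunosuppression and groups infection prophylaxis with the latter.

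Under either option, bring Sections 8.2.1 and 5.7.2 (reason 4) into line with the choice.

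Separately, state one meaning of 'related' and reconcile Table 4, Sections 6.2.1(1), 6.2.2(1) and 6.2.2(2), and the 'certainly' wording in 8.2.2 and 8.3.1 with it. Which codes should lead to a site hold is for the sponsor and the DSMB to settle. The request here is only that the text give one answer.

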**Table 4: Attribution of adverse events**

Code	Descriptor	Definition
UNRELATED CATEGORY		
1	Unrelated	The AE is clearly not related to the allogeneic islets; the islet transplant procedure; immunosuppression or infection prophylaxis; or secondary investigational agent.
RELATED CATEGORIES		
2	Unlikely	The AE is doubtfully related to the allogeneic islets; the islet transplant procedure; immunosuppression or infection prophylaxis; or secondary investigational agent.
3	Possible	The AE may be related to the allogeneic islets; the islet transplant procedure; immunosuppression or infection prophylaxis; or secondary investigational agent.
4	Probable	The AE is likely related to the allogeneic islets; the islet transplant procedure; immunosuppression or infection prophylaxis; or secondary investigational agent.
5	Definite	The AE is clearly related to the allogeneic islets; the islet transplant procedure; immunosuppression or infection prophylaxis; or secondary investigational agent.

For additional information and a printable version of the *CIT-TCAE* manual, consult the *CIT* website: <http://isletstudy.org>.

### 8.3 Serious Adverse Events

#### 8.3.1 Collecting Procedure

SAEs will be collected following the subject's signing of the enrollment consent to participate in the study until 56 days after the subject completes or withdraws from the study. SAEs will be followed until the time the event is resolved, stabilized, or until 56 days after the subject completes or withdraws from the study, whichever comes first.

In addition, SAEs that occur after this time period that are believed to be certainly, probably, or possibly related to the investigational agent will be collected.

For transplants that occur as a standard of care procedure at the University of Alberta, serious adverse events will be collected and submitted by the site investigator until all CIT04 study visits have been completed. If a subject enrolls in a non-CIT islet transplant study, serious adverse events will no longer be collected in CIT starting at the time of the non-CIT study

intervention. All serious adverse event reporting from that point on will be done through the non-CIT study.

The sponsor will request copies of serious adverse events that occur in the non-CIT study from the Principal Investigator for informational purposes.

### 8.3.2 Recording Procedure

SAEs will be recorded on the AE eCRF.

If the investigator believes that an SAE is not related to the investigational product, but is potentially related to the conditions of the study (such as withdrawal of previous therapy, or complication of a trial procedure), the relationship should be specified in the narrative section of the SAE page of the CRF.

### 8.3.3 Reporting Procedure

The following process for reporting an SAE ensures compliance with the ICH guidelines and 21CFR §312.32.

#### 8.3.3.1 REPORTING CRITERIA FROM SPONSOR TO HEALTH AUTHORITY

After the SAE has been assessed, the event will be reported to the appropriate health authorities in the required manner based on the following criteria:

- **No reporting.** This requirement applies if the AE is deemed not serious by the DCC medical reviewer and the NIAID/NIDDK medical monitor.
- **Standard reporting** (i.e., will be included in the investigational new drug [IND] annual report to the health authorities). This requirement applies if the AE is classified as any of the following:
  - Serious, expected, and drug related.
  - Serious, expected, and *not* drug related.
  - Serious, *unexpected*, and not drug related.
- **Expedited reporting.** This requirement applies if the AE is considered serious, unexpected, and drug related as defined in 21 CFR §312.32. This type of SAE must be reported by the sponsor to the appropriate health authorities within 15 days; fatal or life-threatening events must be reported within 7 days.

#### 8.3.3.2 REPORTING TIMELINE- FROM THE SITE TO THE DCC

When an investigator identifies an SAE (as defined in section 8.1.2), he or she must notify the DCC Safety Reporting Center within 24 hours of discovering the event by submitting an initial

electronic SAE CRF. In the event that the eCRF cannot be submitted (i.e., computer failure), the site must fax a paper SAE report to the DCC within 24 hours of discovering the event.

AEs as defined in Section 8.1.1 other than serious AEs will be reported to the DCC by the sites on at least a monthly basis.

#### 8.3.3.3 REPORTING TIMELINE – FROM THE DCC TO THE SPONSOR AND HEALTH AUTHORITIES

The DCC is responsible for notifying the sponsor within 2 business days of receiving the report by the clinical site. The sponsor is responsible for disseminating reports to the health authorities, all investigators in the study, and the manufacturer of the secondary study drug(s). SAEs per 21 CFR §312.32 definitions, except elective hospitalizations, will be reported to the Health Authority by the study sponsor (NIAID) in accordance with applicable regulations.

#### 8.3.3.4 NOTIFYING THE DATA AND SAFETY MONITORING BOARD

The NIAID/NIDDK will provide the DSMB with listings of all AEs/SAEs on an ongoing basis, at least yearly.

#### 8.3.3.5 NOTIFYING THE INSTITUTIONAL REVIEW BOARD AND ETHICS COMMITTEE

The investigator will ensure the timely dissemination of SAE information, including expedited reports, to the IRB and Ethics Committee (EC) in accordance with applicable regulations and guidelines.

#### 8.3.3.6 PREGNANCY

Sexually-active WOCBP must use an effective method of birth control during the course of the study, in a manner such that risk of failure is minimized. Prior to study enrollment, WOCBP must be advised of the importance of avoiding pregnancy during trial participation and the potential risk factors for an unintentional pregnancy. The subject must sign an informed consent form documenting this discussion.

Pregnancy testing must also be performed throughout the study prior to the infusion with NULOJIX® (belatacept) and the results of all pregnancy tests (positive or negative) recorded on the CRF. All WOCBP MUST have a negative serum pregnancy test within 72 hours prior to receiving the investigational product (belatacept). The minimum sensitivity of the pregnancy test must be 25 IU/L or equivalent units of HCG. If the pregnancy test is positive, the subject must not receive the investigational product, and must not be enrolled in the study.

In addition, all WOCBP should be instructed to contact the investigator immediately if they suspect that they might be pregnant (e.g., missed or late menstrual period) at any time during study participation.

If following initiation of study treatment, it is subsequently discovered that a subject is pregnant or may have been pregnant at the time of investigational product exposure, including during at least 56 days after product administration, the investigational product will be permanently discontinued. The investigator will be provided with Pregnancy Surveillance Forms. Upon completion, the form should immediately be sent to the DCC, from where it will be forwarded to NIH and BMS.

Protocol-required procedures for study discontinuation and follow-up must be performed on the subject unless contraindicated by pregnancy (e.g., x-ray studies). Other appropriate pregnancy follow-up procedures should be considered if indicated. In addition, the investigator must report on the appropriate BMS Pregnancy Surveillance Forms(s), follow-up information regarding the course of the pregnancy, including perinatal and neonatal outcome. Infants should be followed for a minimum of 8 weeks. This pregnancy surveillance procedure includes male subjects who fathered a child while receiving study medication; however, male subjects do not need to discontinue study medication.

